6.0 Patient Population

6.1 Eligibility

Patients selected for participation in this Registry should be from the investigator's general ICD population. Data will be collected indicating if a patient receives the S-ICD for primary versus secondary prevention of SCD. Each investigator is responsible for screening all patients and selecting those who are appropriate for inclusion. Patients enrolled in the Registry must meet all inclusion criteria and none of the exclusion criteria as described below.

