Design:	
EFFORTLESS S-ICD is an observational, prospective, non-randomized Registry that will be conducted at approximately 50 clinical centres worldwide. Approximately 1000 patients implanted with, or meeting eligibility criteria for the implantation of the S-ICD system will be enrolled and followed per standard of care for up to 60 months post implant.
	
Primary Objective:	
To demonstrate the early, mid- and long-term clinical outcome of the S-ICD system.
	
Registry Endpoints	
 • Perioperative (30 days post implant) Complication-Free Rate • 360-day Complication-Free Rate • Percentage of Inappropriate Shocks for AF/SVT 	
Observational Data Collection	
 • Clinical Indications for implant • Patient demographics • Type of anesthesia/analgesia • Implant procedure duration • Use of fluoroscopy and X-Ray • Shock conversion efficacies (spontaneous & induced) • All cause therapies (appropriate & inappropriate) 	
 • Overall complication rates with time • Frequency of scheduled/unscheduled follow-ups/hospitalizations • All cause mortality • Length of hospital stay (implant procedure and follow-ups) • All clinical events • Clinical event rates over time • Quality of Life

	
 Total shock burden 	
 Hospital personnel implant and follow-up experience (using surveys)
Sample Size:	The target sample size is approximately 1000 patients.	
Registry Duration:	The expected duration, from enrolment to closure of the main Registry, will be approximately 108 months.	
Patient Selection:	Patients from the investigators' general implantable cardioverter-defibrillator (ICD) patient population will be eligible to be enrolled in this Registry. Patients should meet all the inclusion criteria and none of the exclusion criteria. Retrospective enrolments are allowed providing minimal data requirements are met.	

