5.0 Statistical Methods and Analysis

The statistical analyses related to this Registry including the Sub-Study (see Appendix E) will be executed by the Boston Scientific Clinical Department and/or consultants working on behalf of Boston Scientific. All patients enrolled in the Registry will be included in the analysis. As an observational non-randomized single arm evaluation, the statistical analyses will be descriptive.

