5.9 Retrospective Enrolment Minimal Dataset Requirements

The Registry protocol does allow for the retrospective enrolment of patients already implanted with a Boston Scientific S-ICD system. There are some specific criteria associated with these enrolments that must be fulfilled prior to the enrolment of a retrospective patient:

- The patient meets all the inclusion criteria and none of the exclusion criteria as listed in sections 6.1.1 and 6.1.2
- The patient must be a commercial patient, i.e. they have been implanted with the S-ICD system since the CE mark approval of the device (June 2009).
- The patient has been implanted with a device initially equipped with SW version 1.59.0 or later
- Details of all clinical events (including death as necessary) and all spontaneous episodes that received therapy since implant, are available in medical files or equivalent
- Details of all system related clinical events/hospitalizations and deaths since implant are available in medical files or equivalent

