6.1.1 Inclusion Criteria

Patients who meet all of the following criteria may be considered for inclusion:

- Eligible for implantation of an S-ICD system per local clinical guidelines or currently implanted with an S-ICD system (SW version 1.59.0 or later*)
- Willing and able to provide written informed consent or have informed consent as provided by a legal representative

**Patients currently implanted must meet minimal dataset requirements to be enrolled as described in Section 5.9*

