12.2 Controlling of Devices

12.2.1 Device Distribution

The S-ICD system will be available for distribution at all centres involved in the clinical investigation, therefore devices will be distributed and tracked per standard processes associated with commercial product.

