Appendix D

Investigator Signature Page

Protocol Title:

Evaluation of E FactOrs ImpacTing Clinical Outcome and Cost EffectiveneSS of the S-ICD – The EFFORTLESS S-ICD Registry

Protocol Version:

AB, dated May 04, 2017

I, the undersigned, have read and understand the protocol specified above and agree on its content. I agree to perform and conduct the trial as described in the protocol and in accordance with applicable laws and regulations. In addition, when applicable, I agree to enlist subinvestigators who also agree to perform and conduct the trial as described in the protocol.

PRINCIPAL INVESTIGATOR:

Name: _____

Signature: _____

Date: _____

In the past the 10-year follow-up has been a key milestone for transvenous ICD systems, as the industry average transvenous ICD longevity is approximately 8 years³⁴ and transvenous lead failures occur around 8-10 years post implant.⁹

The first generation S-ICD (SQ-RX) has a projected longevity of approximately 5 years. However the EFFORTLESS S-ICD Registry documents operational and clinical outcomes only up to 5 years after the implant. For this reason little data is available on the success of S-ICD System replacements. This includes pulse generator replacements because of elective replacement indicator (ERI) battery status and electrode replacements. In addition some patients require over time a system replacement due to an indication change, as for example a need for pacing.

This Sub-Study will extend the Registry in order to collect long-term follow-up data on a subset of EFFORTLESS S-ICD patients to achieve an average of approximately 8 years of follow-up from index procedure. Approximately 200 patients will be enrolled in the Sub-Study at a sub-set of EFFORTLESS S-ICD sites. The Sub-Study patients will preferably be recruited from the active EFFORTLESS S-ICD patient population. Patients, who have already completed the EFFORTLESS S-ICD Registry in the past, shall be considered secondarily for participation in the Sub-Study. To reduce the selection bias, the patients shall be screened and approached for consent consecutively.

The expected duration of the extension phase is approximately 72 months.

The following data will be analysed in addition of the main study endpoints:

Primary Analysis

- Rate of long-term S-ICD system-related adverse events
- S-ICD replacements for functionality (e.g. pacing, CRT, ATP etc.)
- Device longevity

Secondary Analysis

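### The main Registry pools retrospectively enrolled patients, selected without a consecutive rule when their outcomes can already be known, into Endpoints 1-3, so the reported rates can be biased

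*Combined protocol and SAP*

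**What the plan says.** Section 6.1 states: "Each investigator is responsible for screening all patients and selecting those who are appropriate for inclusion". Section 6.1.1 is permissive: "Patients who meet all of the following criteria may be considered for inclusion".

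The synopsis adds: "Retrospective enrolments are allowed providing minimal data requirements are met". Section 5.9 repeats the permission and sets the data condition: "Details of all clinical events (including death as necessary) and all spontaneous episodes that received therapy since implant, are available in medical files or equivalent". Neither place limits the number or share of such patients. Under 6.1.1 a patient enters either as eligible for an S-ICD or as carrying one at the time of enrolment.

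On analysis, section 5.0 says: "All patients enrolled in the Registry will be included in the analysis". Section 5.3 gives Endpoint 1 as a percentage with an exact binomial interval, Endpoint 2 as a Kaplan-Meier estimate and Endpoint 3 as a crude proportion of implanted patients. None is split by prospective or retrospective enrolment.

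For the Sub-Study only, Appendix E says: "To reduce the selection bias, the patients shall be screened and approached for consent consecutively".

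**The concern.** Requiring complete records before retrospective enrolment protects data completeness. It also means that the site can know whether the patient had a complication or an inappropriate shock before deciding whether to approach that patient. Nothing in the text reviewed limits or records that choice. There is no consecutive rule, screening log or count of eligible patients not enrolled. The eligibility summary in section 5.1 covers enrolled patients only. Section 13.2 confines deviations to consent and eligibility violations, so selective enrolment would leave no trace.

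The endpoints are single-arm rates, so selection on outcome passes straight into the estimate, and the planned confidence intervals reflect random error only. The closing paragraph of section 2.0 says the Registry is meant to show whether the device can lower complications and inappropriate therapy relative to transvenous systems. With no concurrent control, a biased rate carries directly into that comparison.

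**Working it through.** **1. The plan's own precision.** Section 5.6 plans for 1000 patients and tabulates up to 900 (1000 x 0.90 after 10% attrition). Exact (Clopper-Pearson) limits at n = 900 are -1.63/+1.33 points at a complication-free rate of 95% and -2.15/+1.88 at 90%. Table 1 prints -1.6/+1.3 and -2.1/+1.9, and all 90 of its cells reproduce to within rounding. For Table 2, 1.96 x sqrt(0.90 x 0.10/900) = 1.96 points, printed as 2.0. The tables are correct as measures of sampling error.

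**2. Who can be selected on outcome.** Prospective patients are enrolled on consent before their outcome exists, so they can be selected only on baseline features. Retrospective patients can be selected on the outcome itself: on Endpoint 1 if implanted more than 30 days earlier, and on Endpoint 2 if implanted more than 360 days earlier.

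**3. Direction for complications.** Section 10.1 names system explant as an example of a complication, and section 5.3 counts Type I complications. Under 8.1, a prospective patient who is explanted has already entered the Registry and is followed until the related events resolve. A retrospective candidate explanted before enrolment no longer carries a system. Read literally, 6.1.1 keeps that person out unless he or she is again eligible for an S-ICD. Patients whose system was replaced or repositioned can still enter. The literal rule therefore removes some patients with complications from the retrospective part only.

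**4. Illustrative size.** Let c be the true complication risk, f the retrospective share, and r the chance that a patient with a complication is enrolled relative to one without. All three are assumptions.

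Observed risk = f x c x r/(c x r + 1 - c) + (1 - f) x c

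Example with c = 5%, f = 50%, r = 0.5: 0.5 x 0.025/0.975 + 0.5 x 0.05 = 3.78%, a bias of 1.22 points. Coverage below is the chance that the nominal 95% exact interval at n = 900 contains the true rate.

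| c | r | Observed risk (f = 50%) | Bias, points | Coverage |
|---|---|---|---|---|
| 5% | 0.9 | 4.76% | 0.24 | 94% |
| 5% | 0.75 | 4.40% | 0.60 | 88% |
| 5% | 0.5 | 3.78% | 1.22 | 60% |
| 10% | 0.9 | 9.55% | 0.45 | 93% |
| 10% | 0.75 | 8.85% | 1.15 | 80% |
| 10% | 0.5 | 7.63% | 2.37 | 31% |

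With r = 1 the bias is 0 and coverage about 95%. Over f = 25% to 100% and r = 0.9 to 0.5, the bias runs from 0.12 to 2.44 points at c = 5% and from 0.23 to 4.74 at c = 10%. At f = 25% and r = 0.9, coverage stays at about 95%. If r exceeds 1 the sign reverses: with c = 5%, f = 50% and r = 1.1, observed risk is 0.5 x 0.055/1.005 + 0.5 x 0.05 = 5.24%.

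**The case against.** Section 6.1 can be read more kindly. It draws patients from the investigator's general ICD population, asks that all be screened, and ties selection to the eligibility criteria; on that reading, appropriate simply means eligible. This is fair, and the text does not invite choice by outcome. But nothing records or checks that the instruction was followed.

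A reader might infer that the reported rates are biased favourably throughout. The documents do not support that. Selection on known outcomes is confined to retrospective patients, whose share may be small. For inappropriate shocks no direction can be derived. For complications the argument rests on a literal reading of one criterion, and section 5.9 does provide for deaths, although how a deceased patient would be enrolled is unclear.

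A reader might also size the bias from assumed coverage of all implants. Take 8% complications among enrolled patients, 70-90% of implants enrolled, and 1.5-2 times the risk in the rest. The true rate is then 8.4% (0.9 x 8 + 0.1 x 12) to 10.4% (0.7 x 8 + 0.3 x 16). All of these inputs are assumptions, and the model treats every non-enrolled implant alike instead of following the retrospective route. Of the six combinations of 70, 80 or 90% with 1.5 or 2 times, only the most extreme (2.4 points) exceeds the -2.0/+1.7 margin that Table 1 gives at 92% and n = 900.

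The Sub-Study rule governs drawing about 200 patients from an existing cohort. It shows that the sponsor recognised selection bias there, not that it had main-Registry complication rates in mind. The analyses are descriptive with no pass/fail threshold, so the consequence is for interpretation. The monitoring plan (12.1) and site agreements (11.3) were not supplied, and sections 11.1 and 12.2.2 could not be read, so a site-level safeguard cannot be excluded.

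**Conclusion.** The point holds in limited form and should be addressed. As written, the plan pools patients whose outcomes can be known at selection with patients followed from implant. It has no consecutive rule for the main Registry and no analysis that would reveal a difference. Rates in the retrospective part can be biased, and a favourable direction is plausible for complications only.

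The size is unknown because the retrospective share and the strength of any selection are not stated. With half the patients retrospective and r from 0.9 to 0.5, it is about 0.2-1.2 points at a 5% true risk and 0.5-2.4 at 10%. The lower ends are negligible beside Table 1; the upper end at 10% exceeds the lower arm of 2.1 points at n = 900. The documents do not show that bias occurred, and the plan gives a reader no means of telling which case applies.

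**What to change.** 1. In section 5.3, report Endpoints 1-3 separately for prospective and retrospective patients, state the number in each group, and give the prospective-only result as a sensitivity analysis. This also works for patients already enrolled. A difference would not by itself prove selection, since retrospective implants may be earlier ones, but the reader could then judge.

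2. For any further enrolment, extend the Sub-Study's consecutive rule to 6.1 and 5.9. A site enrolling retrospectively would approach every eligible S-ICD patient implanted since a stated date, including those since explanted; 6.1.1 would need matching wording.

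3. Where centre implant counts can be obtained, report enrolled/implanted by centre as a descriptive check, without a fixed coverage cut-off. Section 12.2.1 says only that "devices will be distributed and tracked per standard processes associated with commercial product", which does not establish that tracking yields eligible implants per centre. Distributed units could include replacements and ineligible patients.

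The cost is a little extra analysis and site work, and wider intervals for the prospective-only estimates. If half of 900 were prospective (450), Table 1 at 95% puts the interval between -2.6/+1.9 (n = 400) and -2.3/+1.7 (n = 500), against -1.6/+1.3 for all 900. This version is dated May 2017 and does not state whether enrolment is still open; if it has closed, items 1 and 3 remain.

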6.1.1 Inclusion Criteria

Patients who meet all of the following criteria may be considered for inclusion:

- Eligible for implantation of an S-ICD system per local clinical guidelines or currently implanted with an S-ICD system (SW version 1.59.0 or later*)
- Willing and able to provide written informed consent or have informed consent as provided by a legal representative

**Patients currently implanted must meet minimal dataset requirements to be enrolled as described in Section 5.9*

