5.3 Registry Endpoints

- **Registry Endpoint 1:** 30-Day S-ICD Complication-Free Rate*, will be summarized as the number of subjects and the percentages relative to the Registry population including the corresponding 95.0% two-sided exact binomial confidence interval.
- **Registry Endpoint 2:** 360-Day S-ICD Complication-Free Rate*, will be analyzed using the Kaplan-Meier (KM) estimate and its corresponding 95.0% confidence interval based on Peto estimate of the standard error.
- **Registry Endpoint 3:** The Percentage of Inappropriate Shocks for AF/SVT, will be analyzed by dividing the number of patients who received at least one inappropriate shock over the total number implanted patients. The mean, median and inter-quartile follow-up time will also be presented.

**Type I Complications will be considered to count towards the complication rate endpoints (see section 10.2). Events related to normal device function e.g. battery deletion within acceptable margins, will not count against the endpoints*

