5.7 Missing Data

Every effort will be utilized to minimize missing data. The number of data for each variable presented will be stated. The number of patients withdrawing from the Registry will be presented with their corresponding time of discontinuation. Time-to-event drop-outs will be censored, consistent with the Kaplan-Meier approach. Any data outside follow-up time period tolerance that was used for analysis will be noted with results presented.

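### Permanent Type I removals before consent appear to be shut out of retrospective enrolment, which pushes the pooled 360-day complication-free rate upward by an unknown, possibly zero, amount

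*Combined protocol and SAP*

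**What the plan says.** Section 6.1.1 has two routes in: "Eligible for implantation of an S-ICD system per local clinical guidelines or currently implanted with an S-ICD system". Its footnote sends the second group to Section 5.9: "Patients currently implanted must meet minimal dataset requirements to be enrolled as described in Section 5.9". Section 5.9 in turn requires of a retrospective enrolment that "The patient meets all the inclusion criteria and none of the exclusion criteria as listed in sections 6.1.1 and 6.1.2". It also asks that "Details of all system related clinical events/hospitalizations and deaths since implant are available in medical files or equivalent". Under Section 7.2, enrolment occurs at written consent.

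On analysis, Section 5.0 states "All patients enrolled in the Registry will be included in the analysis". Under Section 5.3, "Type I Complications will be considered to count towards the complication rate endpoints". Endpoint 1 is a percentage of the Registry population with an exact interval. Endpoint 2 is a Kaplan-Meier estimate with a "corresponding 95.0% confidence interval based on Peto estimate of the standard error". Section 5.7 adds "Time-to-event drop-outs will be censored, consistent with the Kaplan-Meier approach". Section 10.1 lists system explant as an example of a complication, and Section 8.1 keeps a patient explanted after enrolment under observation until the related events resolve.

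Nothing in the documents provides for delayed entry at consent, a split by enrolment route, a cap on the retrospective share, or a count of implanted patients who were not enrolled.

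**The concern.** A retrospective patient brings history from implant but enters only if still carrying a device at consent, on the natural reading. One whose system was removed for good because of a Type I complication before consent is then absent from numerator and denominator. A prospective patient with the same event is counted as a failure. This is left truncation, and the plan handles only right-censoring.

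At stake is how the published complication-free rates can be read. The shift does not shrink as the Registry grows, and neither the exact nor the Peto interval reflects it. Section 2.0 says the Registry is meant to evaluate whether the S-ICD can reduce complications relative to transvenous systems, so uncounted removals bear on that reading. No pass/fail rule depends on the result.

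**Working it through.** **1. The plan's own precision figures.** With no censoring, the Peto half-width is 1.96·S·√[(1−S)/(n·S)]. For S = 0.90 and n = 900 it is 1.96 points (Table 2: 2.0); for S = 0.70 and n = 100 it is 8.98 (Table 2: 9.0). The exact interval at 95%, n = 900, is −1.6/+1.3, as in Table 1. The tables are sound.

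**2. Inputs the documents do not give (all assumed).** C = true 360-day Type I complication probability, 0.10. Half of the events are uniform on days 0–30 and half on days 30–360. r = retrospective share of those enrolled. f = share of Type I complications ending in permanent removal, taken as immediate. Consent for retrospective patients is uniform on days 30–720. n = 900, with no dropout.

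**3. Share lost.** Every removal in the first 30 days precedes consent. A removal on days 30–360 precedes consent with probability 1 − 165/690 = 0.761. So the share of retrospective candidates lost is x = 0.05f + 0.05f × 0.761 = 0.0880f, of which y = 0.0380f had passed day 30 without a complication.

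**4. Bias.**
- Endpoint 2: r·[0.90/(1−x) − 0.90]
- Endpoint 1: r·[(0.95−y)/(1−x) − 0.95]

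Example, r = 50%, f = 25%: x = 0.0220 and y = 0.0095. Endpoint 2: 0.5 × (0.9203 − 0.90) = +1.0 point. Endpoint 1: 0.5 × (0.9617 − 0.95) = +0.6 point.

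| r | f | Endpoint 2 bias (points) | Peto coverage | Endpoint 1 bias (points) | Exact coverage |
|---|---|---|---|---|---|
| 20% | 10% | +0.16 | 94.5% | +0.1 | 95% |
| 20% | 25% | +0.4 | 93% | +0.2 | 94% |
| 50% | 10% | +0.4 | 93% | +0.2 | 95% |
| 50% | 25% | +1.0 | 80% | +0.6 | 89% |
| 50% | 50% | +2.1 | 39% | +1.2 | 61% |

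Coverage is from 10,000 simulated registries per row; the simulated biases agree with the formulas.

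**5. Other assumed settings for Endpoint 2.** With consent on days 30–360, a 60-day lag to removal, r = 50% and f = 25%: +0.7 point, coverage 88%. With a true rate of 80%: +0.3 (r = 20%, f = 10%) and +1.8 (r = 50%, f = 25%), against a half-width of 2.6.

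**6. Endpoint 1 when only events after day 30 end in removal.** Then every lost patient is a 30-day success and x = y = 0.0380f. At r = 50%, f = 25%: 0.5 × (0.9405/0.9905 − 0.95) = −0.02 point. At f = 50%: 0.5 × (0.9310/0.9810 − 0.95) = −0.05 point. Simulation gives about −0.02 to −0.04. Endpoint 2 stays upward.

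**7. Removals after day 360.** These are lost successes for Endpoint 2. Among 1,000 patients at 90%, losing ten who failed by day 360 gives 900/990, or +0.91 point. Losing ten whose removal came later gives 890/990, or −0.10 point. The two cancel at about nine late losses for each early one.

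**8. Explants that are not Type I.** Suppose 3% are explanted for good by day 360, a share q of those explants is Type I, and all precede consent. With f = 0.03q/0.10 and g = 0.03(1−q), the Endpoint 2 bias is r·[(0.90−g)/(1−0.10f−g) − 0.90]. At r = 50% this gives +1.39 (q = 100%), +0.62 (50%), +0.23 (25%), 0.00 (10%) and −0.15 (0%). The break-even is q = C.

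**The case against.** The strongest objection is that the reading is not settled. The two routes in Section 6.1.1 are alternatives, and the first does not say that the patient must never have had a device. Other bullets in Section 5.9 speak of having been implanted, not of still being so. Section 5.9 asks for details of deaths, and Table 3 has a Deaths entry in the Enrolment column. Both fit poorly with a strict requirement to be alive with a device at consent. This stands: the footnote makes the current-implant route the natural one for retrospective patients, but the mechanism may not exist as described. Nor does any single sentence state the time origin for retrospective patients; pooling from implant follows from Sections 5.0, 5.3, 5.7 and 5.9 together.

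Second, the size is assumed throughout. Complications include repositioning and other surgery, and patients revised or re-implanted before consent still enter with their events. Nothing in the documents supports f of 25–50%, which produces the poor coverages. This also stands.

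Third, a reader might infer that both endpoints are certainly inflated, or that the Registry's net bias is upward. The documents support neither. Endpoint 1 can move slightly down (step 6). Explants that are not Type I pull the other way (step 8), and the documents do not say how explants divide between types. Section 6.1 leaves selection to investigators, and the main Registry lacks the consecutive-approach rule that Appendix E sets for the Sub-Study. That selection could act in either direction and is not covered by the figures above.

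What the objection does not remove is that the plan offers no display from which a reader could see whether enrolment route matters.

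**Conclusion.** The point holds in limited form. On the natural reading, permanent Type I removals before consent are lost while the same events after enrolment count. Losing those that occur by day 360 pushes Endpoint 2 upward. The sign for Endpoint 1 is not fixed by the documents: it is upward only if some complications in the first 30 days end in permanent removal before consent.

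The size is not derivable, because the retrospective share, the removal share and the consent gap are not given; it is zero if no such patient exists. Under the assumed ranges (true rate 90%, r = 20–50%, f = 10–50%) Endpoint 2 is high by about 0.2 to 2.1 points, from negligible up to the full Table 2 half-width. Severity is minor to moderate: the Registry is single-arm and descriptive, and no decision rule turns on these rates.

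**What to change.** 1. Reconcile the current-implant condition in Section 6.1.1 with the two mentions of death in Section 5.9 and with the Deaths entry in the Enrolment column of Table 3, so that it is clear whether a patient no longer carrying a device could be enrolled retrospectively.
2. In Section 5.3, keep the pooled all-enrolled result. Beside it report Endpoints 1 and 2, with counts, separately for patients consented before implant and for retrospective patients. Name the consented-before-implant estimate as the one free of this selection. If item 1 confirms that a device at consent was required, say so with the results.
3. Optional sensitivity analysis: a Kaplan-Meier estimate for Endpoint 2 in which retrospective patients join the risk set at consent. Use Greenwood standard errors; in simulation at r = 50%, Peto coverage under delayed entry was only about 91%. This analysis assumes that consent time is unrelated to risk and gains little: half-width 2.6 against 2.8 for consented-before-implant only (r = 50%), and about 2.2 for both at r = 20%.

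Cost: Section 13.4 requires written notice with reasons to all Principal Investigators, and ethics committee approval as required. The split uses implant and consent dates and needs no new visit. The price is wider intervals in each group. At r = 50% of 900, Endpoint 1 at 95% on 450 patients has limits of about −2.4/+1.8 instead of −1.6/+1.3, and the Endpoint 2 half-width at 90% is about 2.8 instead of 2.0.
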